# 5.1.7. Level of Significance

For the primary efficacy endpoint analysis, the statistical comparison will be conducted using an exact binomial test against a fixed external control value of 1% at a one-sided Type 1 error rate of 0.05 and applying the Hochberg procedure for adjusting for multiple comparisons (see Section 5.3.4).

For the comparisons between the intervention arms (Arms 1,2), the Mantel-Haenszel test adjusting for the stratification factor will be used in a secondary analysis to compare the primary endpoint between the intervention arms at a one-sided alpha level of 0.05.

For all other efficacy analyses, only two-sided 90% CIs will be provided with no adjustment for multiplicity, unless otherwise specified.

# 5.1.8. Missing and Partial Dates Imputation Rules

For analysis and reporting purposes, missing or partial dates in adverse event (AE onset date; AE end date), HBV diagnosis and infection dates, concomitant therapies (start date; end date) will be imputed according to the rules in the following subsections. The original, non-imputed, dates will be used only in listings.

# 5.1.8.1. Adverse Event Onset Date and Resolution Date

Partial AE onset dates will be imputed as follows:

- If the AE onset date is missing the day only, it will be set to:
  - The first day of the month when the AE occurred, if month/year of the AE onset date is different than the month/year of the first administration of study agent date.
  - The day of the first study agent administration, if the month/year of the AE onset date is the same as the month/year of the first study agent administration but the month/year of the AE resolution date is different.
  - The earliest between the day of the first study agent administration date and day of AE resolution date, if month/year of the AE onset are the same as both the month/year of the first study drug administration and the AE resolution date.
- If the AE onset date is missing both day and month, it will be set to the earliest of:
  - January 1 of the year of onset, as long as this date is on or after the first study drug administration.
  - Month and day of the first study agent administration, if this date is in the same year of AE onset date.
  - December 31 if the AE onset date year is prior to the year of the first study drug administration.
  - The AE resolution date.

• Completely missing onset dates will not be imputed.

Partial AE resolution dates not marked as ongoing will be imputed as follows:

- If the resolution date of an AE is missing the day only, it will be set to the earliest of the last day of that month or the day of the date of death, if the participant died in that month.
- If the resolution date of an AE is missing both day and month, it will be set to the earliest of December 31 of that year or the day and month of the date of death, if the participant died in that year.
- Completely missing resolution dates will not be imputed.

# 5.1.8.2. HBV Diagnosis and Infection Dates

If the reported date is partially missing, the following imputation rules will be applied:

- the 15th of the month, if only the day is missing.
- the 30th of June, if only the year is available.
- No imputation if completely missing.

# 5.1.8.3. Concomitant Medication Dates

In case of partially missing concomitant medication start/end dates, the following imputation rules will be applied:

- the 15th of the month, if only the day is missing.
- the 30th of June, if only the year is available.
- If the imputed start date is after the concomitant medication end date, further adjustment of the imputed start date is required. It will be imputed as the concomitant medication end date.
  - No imputation if completely missing.

If the medication was taken prior to study start (SI Day 1) based on eCRF question, and the imputed start date is after first treatment date, further adjustment of the imputed start date is required. It will be imputed as the day prior to first dosing date.

If the medication was taken after study start (SI Day 1) based on eCRF question, and the imputed start date is prior to first dosing date, the imputed start date will be further adjusted to be the first study agent dosing date. The partially missing medication end date will be imputed following the rule described at the beginning of this section to ensure it is on or after first dosing date, and after its start date.

- In case of a completely missing start date, the concomitant therapy will be considered as having started before the trial, unless the eCRF indicating that the medication was taken after study start.
- In case of a completely missing end date, the concomitant therapy will be considered as ongoing at the end of the trial, unless the eCRF indicating not ongoing.

## 5.1.8.4. Dates of Alcohol Consumptions

In case of partially missing start/end dates, the following imputation rules will be applied:

- the 15th of the month, if only the day is missing.
- the 30th of June, if only the year is available.
- If the imputed start date is after the end date, further adjustment of the imputed start date is required. It will be imputed as the end date.
- If end date is completely missing and marked as Ongoing then impute with randomization date. Otherwise, no imputation if completely missing.

#### 5.1.9. Data Handling Rules

Those measurements collected from screening visit to the end of study will be handled according to the following rules summarized in Table 4.

HBV parameter	LLOQ	ULOQ	Imputed Values	
			If value< LLOQ	If value> ULOQ
HBsAg	0.05 IU/mL	249,750.00 IU/mL with dilution	0.025 IU/mL (a)	274,725.00IU/mL (b) with dilution
HBeAg	0.11 IU/mL	7,000.00 IU/mL with dilution	0.055 IU/mL (a)	7,700.00 IU/mL (b) with dilution
HBcrAg*	3.0 log 10 U/mL	9.0 log 10 U/mL with dilution	2.7 log 10 U/mL	9.9 log 10 U/mL (b) with dilution
HBV DNA	20 IU/mL	170,000,000 IU/mL w/o dilution	If target detected: 15 IU/mL** If target not detected: 5 IU/mL**	187,000,000 (b)(c) IU/mL w/o dilution
HBV RNA*	LLOQ = $2.939$ log 10 cp/mL (i.e. 869 cp/mL) LOD = $1.398$ log 10 cp/mL (i.e. 25 cp/mL)	NAP	If <lod or="" target
not detected then 1.114 log10 cp/mL (13 cp/mL)</lod>	NAP
Anti-HBs	5 mIU/mL	10000.0 mIU/mL	2.5 mIU/mL(a)	11000.0 mIU/mL (b)

 Table 4:
 Data Handling Rules for HBV Virology and Serology Assessments

#### Table 4: Data Handling Rules for HBV Virology and Serology Assessments

HBV parameter	LLOQ	ULOQ	Imputed Values	
			If value< LLOQ	If value> ULOQ

\* As new assays become available different data handling rules may apply.

\*\* For HBV DNA spaghetti plots showing absolute values, the imputed value will be 15 IU/mL. For all other tables, listings and figures, the main analysis will be performed using 15 IU/mL to impute HBV

DNA<LLOQ and the two methods of imputation may be used as exploratory analysis.

Key: NAP=Not applicable

- (a) LLOQ/2
- (b) ULOQ+(ULOQ/10)
- (c) If the original result > ULOQ, then take the re-test value (i.e., diluted result). If the diluted result is not available, use the imputed value indicated in this table.

All other viral activity data with values <LLOQ which are not included in the data handling rules above will be imputed by the absolute value divided by 2.

#### 5.2. Participant Dispositions

All the summaries will be done on the FAS analysis set unless specified otherwise.

Screened participants and reason for screen failures will be summarized overall.

The number of participants in the following disposition categories will be summarized throughout the study by intervention group and overall:

- Participants randomized
- Participants who received any study intervention (JNJ-3989, Nivolumab)
- Participants in each study analysis phase
- Participants who completed the study
- Participants who completed study intervention but dropped off during follow-up
- Participants who discontinued any study intervention
- Reasons for discontinuation of any study intervention
- Participants who terminated study prematurely
- Reasons for termination of study

A listing of participants will be provided for the following categories:

- Participants who discontinued any study intervention
- Participants who terminated study prematurely
- Participants who were randomized yet did not receive study intervention.

#### 5.3. Primary Efficacy Endpoint

#### 5.3.1. Definition

The primary endpoint is the proportion of participants who achieved HBsAg seroclearance (HBsAg<LLOQ) at FU Week 24.

## 5.3.2. Main Estimand for the Primary Endpoint

**Study Objective:** To evaluate the efficacy in terms of HBsAg seroclearance for the treatment regimens of JNJ-3989 + nivolumab at Week 16 + NA (Arm 1), and JNJ-3989 + nivolumab at Weeks 16, 20, 24 + NA (Arm 2), as compared to JNJ-3989 + NA.

Scientific Question of Interest: in HBeAg negative virologically suppressed adult population with chronic HBV infection

- a) Comparison vs fixed external control: what is the benefit of JNJ-3989 + nivolumab (1 or 3 infusions) + NA compared with a fixed external proportion of 1% for JNJ-3989 + NA, measured by proportion of participants achieving HBsAg seroclearance at FU Week 24?
- b) Comparison amongst regimens: what is the difference between JNJ-3989 + nivolumab (1 infusion) + NA and JNJ-3989 + nivolumab (3 infusions) + NA, measured by proportion of participants achieving HBsAg seroclearance at FU Week 24?

The attributes for the main estimand for the primary endpoint are:

## A) Study Intervention Arms:

- Arm 1: JNJ-3989 + nivolumab (1 infusion) + NA
- Arm 2: JNJ-3989 + nivolumab (3 infusions) + NA
- **B)** Study Population: HBeAg-negative chronic HBV-infected adult patients who are virologically suppressed by being treated with NA.
- **C) Variable:** Individual participant response status defined as whether an individual participant achieved HBsAg seroclearance at FU Week 24 (responders) as detailed in Section 5.3.1.

## **D)** Intercurrent events:

- Treatment discontinuation prior to Week 24: if the participant discontinued treatment prior to Week 24 then s/he will be considered non-responder (composite strategy).
- Major protocol deviations affecting efficacy: Table 9 identifies the deviations considered intercurrent event. Participants with such deviations and who have missing data for the endpoint will be considered as non-responders (composite strategy). For all other deviations not considered intercurrent events, the data are used regardless of the occurrence of major protocol deviations (treatment policy strategy).

- Deaths prior to FU Week 24 are handled in a composite strategy as participants who die prior to FU Week 24 will be considered as non-responders.
- **E)** Population-level summary:
  - **a. Primary (comparison vs fixed external proportion):** Difference in proportion of participants with HBsAg seroclearance at FU Week 24 using a fixed external proportion of 1%.
  - **b.** Secondary (comparison amongst regimens): Difference in proportion of participants with HBsAg seroclearance at FU Week 24 between study intervention arms.

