Overall rationale of this SAP Amendment: The main reason for this SAP amendment was to align with the protocol amendment 2 that was performed due to difficult recruitment. Therefore, a strategic decision was taken to not extend further enrollment beyond the planned enrollment period and continue the study with a reduced sample size. In the meantime, there has been a new amendment (amendment 3 – 30 June 2023) of the protocol filed. The main reason for the protocol amendment 3 was the discontinuation of PD-1 inhibitor (nivolumab) as study intervention as of 20 June 2023 as an urgent safety measure (USM). Based on the observation of two cases of potential hyperthyroidism, the sponsor decided on 20 June 2023, to halt further nivolumab dosing effective immediately. Treatment with JNJ-3989 and/or nucleos(t)ide analog was continued as planned. The impact of this amendment 3 has been discussed and it has been agreed that this does not affect the Statistical Analysis Plan.

Section number and Name	Description of Change	Brief Rationale
1.2. Study Design	Reduction of	Due to difficult
	sample size.	recruitment.
3. Sample Size		
Determination		
5.1.9. Data Handling Rules	Revised ULOQ and Imputed Values	Improved for clarity
	data cutpoints for HBsAg, HBeAg	and precision.
	and HBcrAg.	
	Updated guidelines for the	
	imputation of HBV DNA.	
5.5.1.1.5. Anti-HBe	Analysis removed.	Qualitative anti-HBs
Antibodies		results are not
		collected.

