#### Statistical Analysis Plan 73763989PAHPB2008

Section number and Name	Description of Change	Brief Rationale
		decided to remove some subgroups.
6.4. Appendix 4 Protocol Deviations	List was updated to incorporate the updated list as per protocol amendment #3.	For completeness

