## 1. INTRODUCTION

The statistical analysis plan (SAP) for the 73763989PAHPB2008 phase 2 trial describes the statistical analyses, and definitions to assess the efficacy, safety, tolerability, and pharmacodynamics of the combination of JNJ-73763989 (JNJ-3989), nucleos(t)ide analogs (NAs), and nivolumab in virologically suppressed, HBeAg-negative, chronic HBV-infected (CHB), adult participants < 56 years of age.

This study is part of the platform trial PLATFORMPAHPB2001 in participants with CHB. The protocol for 73763989PAHPB2008 constitutes the Intervention Specific Appendix 7 that describes all the specific and/or additional features of this study complementing the common design elements of the platform trial described in the Master Protocol.

This SAP is to be interpreted in conjunction with the clinical trial protocol amendment 1 finalized on 30 June 2022, and with the Master Protocol Amendment-3 for PLATFORMPAHPB2001 finalized on 21 January 2021.

Details on pharmacokinetic (PK) and pharmacokinetic/pharmacodynamic (PK/PD) analyses will be described in a separate analysis and modelling plan.

Objectives		Endpoints	
Pri	Primary		
•	To evaluate efficacy of the study intervention, based on HBsAg levels at FU Week 24.	•	Proportion of participants who achieve HBsAg seroclearance at FU Week 24.
Sec	ondary		
•	To characterize the safety and tolerability of the study intervention.	•	Proportion of participants who experienced AEs of interest.
		•	Safety profile of JNJ-3989 with nivolumab throughout the study (safety parameters include but are not limited to the frequency and severity of AEs and immune-related AEs, vital signs measurements, physical examinations, clinical laboratory values, and 12-lead electrocardiograms [ECGs]).
•	To evaluate efficacy in terms of changes in HBsAg levels from baseline over time during the study intervention and follow-up periods.	•	Change from baseline in HBsAg levels during the study intervention and follow-up periods. Proportion of participants with HBsAg levels below/above different cut-offs over time.
•	To evaluate efficacy in terms of HBsAg seroclearance/seroconversion during the study intervention and follow-up periods.	•	Proportion of participants with HBsAg seroclearance/seroconversion during the study intervention and follow-up periods. Time to achieve HBsAg seroclearance/ seroconversion.

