## 5. STATISTICAL ANALYSES

## 5.1. General Considerations

The SAP will use throughout the document the following definitions:

- Study agent refers to: JNJ-3989, and nivolumab
- Study intervention arm refers to:
  - Arm 1: JNJ-3989 + nivolumab (1 infusion) + NA
  - Arm 2: JNJ-3989 + nivolumab (3 infusions) + NA

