# 5.3.2.1.4. Missing Data Handling Rule

Participants who withdraw from the study prior to FU Week 24 will be considered as non-responders.

If a participant remains in the study after experiencing a major protocol deviation (defined for the purpose of efficacy analyses and is an intercurrent event) and has missing FU Week 24 value, then the imputation to non-response will be applied. If the value for the endpoint at FU Week 24 is available, then such data will be used to determine their response status.

For the participants still in the study at FU Week 24 or for participants that have neither discontinued treatment early nor experienced any major protocol violations (defined for the purpose of efficacy analyses and is an intercurrent event), and HBsAg values missing at FU Week 24, then the primary method to handle missing data will be the missing as non-responder (MANR).

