Table 9: Selected Major Protocol Deviations for Analysis Purposes

Sequence number (as reported in MPD)	Description	Protocol Deviation Description (DVTERM) as entered in Study Specific Issue System	Protocol Deviation Coded Term (DVDECOD)	Exclude from PP	Intercurrent Event
	
 
Part of a multivitation formulation.
 
Note: The use of other vitamins is allowed.
 
Topical steroids (>7 days) under occlusive dressing.
 
				
47	Dose of study medication JNJ- 3989 missed or not administered within scheduled time window.	Subject did not receive dose of study drug JNJ-3989 within window. <specify visit
number, if the dose was administered before/after the projected window and number of days out of window></specify>	Received wrong treatment or incorrect dose	If classified as major protocol deviation (reviewed case by case), excluded from PP set.	Yes
48	Dose of study medication Nivolumab missed or not administered within scheduled time window.	Subject did not receive dose of study drug Nivolumab within window. <specify visit
number, if the dose was administered before/after the projected window and number of days out of window></specify>	Received wrong treatment or incorrect dose	If classified as major protocol deviation (reviewed case by case), excluded from PP set.	Yes
52	Volume of JNJ-3989 was not totally injected.	Volume of JNJ-3989 was not totally injected. <specify number,="" the
prescribed volume and the administered value ></specify>	Received wrong treatment or incorrect dose	If classified as major protocol deviation (reviewed case by case), excluded from PP set.	Yes
53	Participant received a wrong dose of study intervention (JNJ- 3989 or nivolumab)	Dose error for <insert Nivolumab or JNJ-3989, specify visit number, the prescribed volume and the administered value ></insert 	Received wrong treatment or incorrect dose	If classified as major protocol deviation (reviewed case by case), excluded from PP set.	Yes
54	Volume of Nivolumab was not totally infused.	Volume of Nivolumab was not totally infused. <specify number,="" the
prescribed volume and the administered value ></specify>	Received wrong treatment or incorrect dose	If classified as major protocol	Yes

 Table 9:
 Selected Major Protocol Deviations for Analysis Purposes

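### Does the primary estimand leave open whether an Arm 2 participant stopped by the June 2023 nivolumab halt is scored a non-responder?

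*SAP*

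**What the plan says.** The main estimand (SAP 5.3.2 D) lists as its first intercurrent event: "Treatment discontinuation prior to Week 24: if the participant discontinued treatment prior to Week 24 then s/he will be considered non-responder (composite strategy"). The supplementary estimand (5.3.3 D) repeats the rule. Neither says which agent. The nearest definition, in SAP 5.1, is "Study agent refers to: JNJ-3989, and nivolumab".

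Deviation-type intercurrent events are handled differently. Table 9 no. 48 covers "Dose of study medication Nivolumab missed or not administered within scheduled time window" and carries the intercurrent-event flag. For such events SAP 5.3.2.1.4 says: "If the value for the endpoint at FU Week 24 is available, then such data will be used to determine their response status".

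The SAP Version History (Amendment 1) records the halt: "The main reason for the protocol amendment 3 was the discontinuation of PD-1 inhibitor (nivolumab) as study intervention as of 20 June 2023". It adds that JNJ-3989 and/or NA went on as planned, and concludes: "The impact of this amendment 3 has been discussed and it has been agreed that this does not affect the Statistical Analysis Plan". The Appendix 4 row of the same log reads: "List was updated to incorporate the updated list as per protocol amendment #3". The Introduction still says: "This SAP is to be interpreted in conjunction with the clinical trial protocol amendment 1 finalized on 30 June 2022".

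**The concern.** JNJ-3989 and nivolumab can stop separately. SAP 1.2 has JNJ-3989 stopping both, but nivolumab stopping alone. The Version History describes the halt with the same word, discontinuation, that triggers non-response in 5.3.2 D. For one kind of participant, the Arm 2 seroclearer halted after one or two infusions, two rules could give opposite results: non-responder under the discontinuation rule read as any agent, responder under the observed-value rule. An Arm 1 participant halted before the Week 16 infusion raises the same question.

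Each arm needs only two responders to reject, so one status can decide an arm's test. The any-agent reading can only remove responders, so it cannot create a false positive against 1%. What would be at stake is a true response lost, or a rule settled once the results were known.

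**Working it through.** **Which reading the text supports**

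- SAP 1.2 has a sentence of the same form as the rule, stopping treatment early before Week 24, and it names JNJ-3989. The nivolumab sentence beside it has no Week 24 anchor.
- Arm 1 receives nivolumab once, at Week 16. Only JNJ-3989 runs to Week 24 in both arms, so a Week 24 limit fits JNJ-3989.
- Protocol section 7 describes the early stop before Week 24 as stopping all study intervention.
- SAP 5.2 and 5.6.2 write *any* when stopping either agent is meant. Section 5.3.2 D does not.
- SAP 5.1.6.2 and 5.1.6.3 date the end of treatment from JNJ-3989.
- The Version History says other treatment continued and the SAP is unaffected. Scoring halted participants as failures would have affected the primary count.

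An analyst who instead treats the omitted infusion as Table 9 no. 48 also reaches the observed value through 5.3.2.1.4. A missing value, or one at or above LLOQ, is non-response under every reading.

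**Reproducing the plan's power**

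Exact one-sided binomial against 1%. The critical count is 2 at both Hochberg levels (0.05 and 0.025) for n=16, 18, 19 and 20. Power = 1 − (1−p)^n − n·p·(1−p)^(n−1). At p = 1% + 15% = 16%: n=20 gives 0.853 and n=16 gives 0.751, matching the stated 85% and 75%.

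**How much one status can matter**

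- Arm 2 (n=19): P(X≥1)=0.174; P(X≥2)=0.0153; P(X≥3)=0.0009.
- Arm 1 (n=18): P(X≥1)=0.165; P(X≥2)=0.0138.
- With 1/18 and 2/19, the larger p (0.165) exceeds 0.05 and the smaller (0.0153) is below 0.025, so Arm 2 is rejected. Recoding one gives 1/18 and 1/19, and nothing is rejected. The Arm 2 90% Clopper-Pearson lower limit moves from 1.90% to 0.27%.
- With 3/19, recoding one leaves 2/19, still rejected.

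**Chance that it matters, if the any-agent reading were used**

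The documents do not give the number halted. By calendar, 20 June 2023 less 24, 20 and 16 weeks is 3 January, 31 January and 28 February 2023. Arm 2 participants randomised between the first two dates were due two infusions before the halt, and those between the last two were due one. Assume k of 19 were halted after one or two infusions, with a common response rate p in both arms and Arm 1 unaffected.

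The Arm 2 test changes when a+b≥2 and b≤1, with a~Bin(k,p) and b~Bin(19−k,p). The hypothesis that at least one regimen works changes only if Arm 1 also has at most 1/18. That has probability 0.7055, 0.3958, 0.1920 and 0.0831 at p=6%, 11%, 16% and 21%. Multiplying the two:

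| k | Result | p=6% | 11% | 16% | 21% |
|---|---|---|---|---|---|
| 1 | Arm 2 test | 0.0226 | 0.0300 | 0.0238 | 0.0144 |
| 1 | Trial conclusion | 0.0160 | 0.0119 | 0.0046 | 0.0012 |
| 2 | Arm 2 test | 0.0454 | 0.0619 | 0.0505 | 0.0317 |
| 2 | Trial conclusion | 0.0320 | 0.0245 | 0.0097 | 0.0026 |
| 4 | Arm 2 test | 0.0909 | 0.1311 | 0.1139 | 0.0766 |
| 4 | Trial conclusion | 0.0641 | 0.0519 | 0.0219 | 0.0064 |

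**Knock-on to visit windows**

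If Table 2 took the Week 16 infusion as the discontinuation date, FU Day 1 would be nominal day 114. The FU Week 16 visit (day 169+112=281) would then have FU day 281−114+1=168, inside the FU Week 24 window [156, 197]. That reading puts later JNJ-3989 doses into follow-up and contradicts 5.1.6.2 and 5.1.6.3, so it is not one an analyst would adopt.

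**The case for a change.** The best case for a change is that no sentence in the available text names the agent, that the halt made the question live, and that the planned analyses do not test it. Sensitivity estimators 2 and 3 keep the same intercurrent-event strategies, and the supplementary estimand repeats the wording. SAP Amendment 2 mentions a low number of observed events, so counts near the threshold are realistic. The log's statement that the SAP is unaffected does not say which rule applies. A clarification would cost a line.

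What stands is that the wording is loose and the reference to protocol amendment 1 is out of date. The rest is weaker. The log and the updated Appendix 4 show that the later amendments were considered. The absence of a Table 9 row for a sponsor-ordered omission is not clearly a gap, since an omission required by an amended protocol need not be a deviation. A clarification now would also postdate the primary analysis, so it could not serve as pre-specification.

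Two related requests do not settle the matter. FAS-N needs only one nivolumab dose, so it keeps those halted after one or two. The SAP's 5% trigger for running it (2/37=5.4% meets it, 1/37=2.7% does not) is a separate choice. A table of response by infusions received would help a reader of the 1-versus-3-infusion comparison, but it splits very small arms by a post-randomisation variable and corrects no error.

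**Conclusion.** No change is called for. The rule omits a word that the surrounding text supplies: treatment here means JNJ-3989, or all study intervention. A participant affected only by the nivolumab halt then keeps the observed FU Week 24 HBsAg result, and the missed-dose route gives the same answer. Stating that reading in the study report is ordinary practice and alters no planned result.

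The residual risk exists only if an analyst took the disfavoured any-agent reading and a halted participant had cleared HBsAg. The trial conclusion would then change only if Arm 2 fell from at least two responders to at most one while Arm 1 had at most one. Under the assumed one to four halted participants and response rates of 6% to 21%, that is about 0.1% to 6.4%, and the error would be conservative against the 1% control. These figures assume equal response rates in the two arms and an unaffected Arm 1. The actual number halted is unknown, and protocol text on the halt may be missing from the version reviewed.
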